Cover page

Trial Title:

**A New Conception About Individualized Treatment
Allocation for HCC—Using Machine Learning**

**Unit of Study: The Second Affiliated Hospital of Air
Force Military Medical University**

Principal Investigator: [name]

Date: 2023-8-20

NCT number and document date have not been assigned

Study protocols

1. Study population

Between January 2010 and October 2021, a total of 5816 consecutive HCC patients receiving LR or TACE from 15 Chinese tertiary hospitals were retrospectively screened. HCC was diagnosed based on either imaging or pathological results as previously described [1]. To better fit LR and TACE therapies into AI models, liver-confined HCC was incorporated with LR or TACE candidates according to the latest criteria of the BCLC guidelines [2]. Patients with well-preserved liver function, good PS (Eastern Cooperative Oncology Group [ECOG] PS0), and no vascular invasion or extrahepatic spread were divided into BCLC 0, A, and B stages, where they could undergo LR and TACE therapy. In addition, mild tumor-related symptoms (PS1) have not been an absolute contraindication for LR as per recent research [3], and the guidelines of the American Association for the Study of Liver Diseases (AASLD) expanded the PS 0–1 in the BCLC 0–B stage, considering the conceptual overlap between them [4, 5]. Here, the inclusion criteria were as follows: (a) diagnosed with HCC; (b) receiving LR or TACE therapy; (c) complete clinical information; (d) preserved liver function (Child-Pugh Score [CPS] ≤ 7); and (e) PS 0–1. The exclusion criteria included: (a) vascular invasion or extrahepatic spread; (b) decompensated liver cirrhosis (gastrointestinal bleeding, ascites, or hepatic encephalopathy); (c) younger than 18 years; and (d) duration of follow-up of fewer than 30 days. Image assessment, including the diameter of the largest nodule (tumor size, measured in centimeters) and tumor number, was performed by two independent investigators via CT or MRI. The flow chart of the study is depicted in Figure 1. Eligible patients were randomly stratified into train and validation cohorts (ratio=0.85: 0.15). The study was approved by the committee on human research of participating centers and approved by the Medical Ethics Committee of the Tangdu hospital (TDLL-202302-06) and Daping Hospital of the Army Medical University (2022(186)). Written informed consent to participate in this study was provided by the participants' legal guardian/next of kin.

2. Treatment procedures

During the LR procedure, patients were placed in the supine position, often under general anesthesia of the trachea. Operators fully exposed the surgical field and explored the location of the tumor and vascular anatomy. After blocking the first liver portal, operators ligated the liver section blood vessels and bile ducts, assessed the distance between lesions, and ensured residual liver volume. Multiple tumors were removed by en bloc resection or multiple LR with good liver function, including indocyanine green (ICG) clearance tests ^[6].

During the TACE procedure, an emulsion of mixtures of lipiodol (3–30 ml) and chemotherapeutic drugs was injected, including doxorubicin (10–50 mg), cisplatin (10–110 mg), epirubicin (10–50 mg), or oxaliplatin (100–200 mg). Afterward, either a gelatin sponge or polyvinyl alcohol foam (PVA) particles were introduced to embolize tumor-feeding vessels either selectively or super-selectively ^[7].

3. Model development

According to survival algorithms in the existing literature, 10 kinds of available AI models were developed in the training set. The details of data preprocessing and model development are shown in Supplement 1. To reduce the overfitting of survival models, the AI algorithms in the training cohort were developed by adopting K-fold cross-validation. In each fold, hyperparameter optimization was tuned by an exhaustive cross-validation grid search, and the models were refitted in the training set with the optimal score parameters. The selection criterion of the AI models was defined as a C-index ≥ 0.7 . Based on the AI models, the predictive performance (censored C-index and mean cumulative/dynamic area under the receiver operating characteristic curve [auROC]), calibration curves, and Brier score (BS) were evaluated. The BS represents the mean square difference between observed patient status and predicted survival probabilities; it ranges from 0 to 1 and is negatively correlated with the discrimination and calibration of algorithms. IBS is defined as an overall estimation of BS; a value lower than 0.25 is deemed applicable in the clinic ^[8].

4. Model estimation

An ensemble model was developed and named the precise treatment allocation (PTA) model in our study. It could accurately predict the survival probability of each patient by alternating the different treatments. The inputs of the PTA model mainly comprise four modules: (a) liver function, such as serum albumin, serum bilirubin, and coagulative function indexes; (b) tumor burden, including serum alpha-fetoprotein (AFP), tumor size, and tumor number; (c) demographic data, such as age and gender; and (d) routine laboratory indications, such as routine blood examination and kidney function indexes. To further estimate the predictive performance of the PTA model, it was compared with other prognostic models, including widespread clinical guidelines (BCLC, BCLC B sub-classification ^[9], HKLC, and the most recent Italian Liver Cancer [ITA.LI.CA] staging system ^[10]), other tumor-burden-based models (up-to-seven model ^[11], four-and-seven model ^[12], and six-and-twelve model ^[13]), and models incorporating other parameters (hepatoma arterialembolization prognostic [HAP] score, modified HAP [mHAP] II score ^[13], mHAP III score ^[14], albumin-bilirubin [ALBI] score ^[15], and the model to estimate survival in ambulatory HCC patients [MESIAH] ^[16]), by estimating the auROC and C-index.

Here, HCC patients could achieve two potential survival rates and predicted median survival times (MSTs) by choosing TACE or LR. The ideal LR candidate is defined as a patient whose MST could be extended by more than 50% compared with the MST of primary treatment if LR is adopted in the model. Similarly, ideal TACE candidates are those with an additional survival benefit of more than 50% compared to LR allocation in TACE prediction time. Considering that BCLC and HKLC ^[17] have clearly defined LR and TACE candidates, the ideal LR and TACE candidates of the PTA model were compared with candidates recommended by these two widely used guidelines.

5. Web implementation

After train and validation, the optimized PTA model was implemented as a web

interface, which generates the MST and depict integrated survival curves composed of LR and TACE according to the clinic parameters of specific patients provided by users. Relative algorithms of web development were described in the supplement 1.

6. Statistical analyses

Continuous and normally distributed variables were expressed as mean with a standard difference (SD) and compared using Student's t-test, while non-normally distributed variables were presented as median with interquartile range (IQR) and compared using the non-parametric Mann–Whitney U test. Categorical variables were expressed as numbers and percentages and tested by Fisher's exact test or the χ^2 test.

Overall survival (OS) was defined as the time interval between initial TACE or LR and all-cause death. Patients who survived up to the last follow-up date (October 15th, 2021) or were lost to follow-up were censored. Survival curves were displayed using the Kaplan–Meier (K-M) method and compared with the log-rank test.

Python software was applied for train AI models and detailed codes were uploaded as supplements (<https://github.com/ApocalypseZ/Survival>). R software and related packages (survival, rms, reportROC, survminer, and ggplot2) were adopted to conduct statistical analysis and plot figures. $P < 0.05$ was considered statistically significant.

Results information for studies

Basic clinical characteristics

In this multicenter study, 4991 patients met the selection criteria and were included. Of these, 1916 patients (38.39%) were amenable to LR while 3075 patients (61.61%) submitted to TACE (Figure 1). 4192 (84%) and 799 (16%) patients were divided into train and validation sets, respectively. Among train set, 1622 (38.7%) were underwent LR while 2570 (61.3%) adopted TACE treatment. In validation set, 294 (36.8%) and 505 (63.2%) were allocated to LR and TACE treatment, respectively. The demographic and clinicopathological characteristics of the cohort are shown in Table 1. The variables associated to tumor burden were lower in the LR group than those of the TACE group in overall cohort: (a) The largest tumor diameters were smaller in the

LR group (4.60 [3.00;7.00] cm) than in the TACE group (6.30 [4.00;9.90] cm); (b) The tumor lesions of HCC were relatively few in the LR group (1.0 [1.0-1.0] lesion) than in the TACE group (1.0 [1.0-2.0] lesions). In addition, the liver function of HCC patients (CPS and Child-Pugh stage) varied remarkably between the LR and TACE groups. A higher proportion of Child stage B patients were included in the TACE group (17.6%) than in the LR group (11.1%). The median follow-up was 54.0 months (IQR 38.7–69.2 months) for LR therapy and 36.1 months (IQR 24.7–54.7 months) for TACE. The 1-year, 3-year, and 5-year survival probability was 91.7%, 79.6%, and 70.8% for LR allocation, respectively, while 74.8%, 41.5%, and 26.4% for TACE treatment, respectively. Although there were significant differences between the LR and TACE groups, we perceived therapy type as a pivotal factor in the AI models to simulate a real-world clinical setting, considering the precise prediction of AI technologies.

Selection of the optimal AI model

We applied 10 kinds of machine learning survival algorithms in the train cohort, of which seven AI models performed well, with the C-index > 0.7 , and were retained: (i) random survival forest (RSF), (ii) conditional survival forest, (iii) DeepSurv algorithm, (iv) Extra Survival Trees, (v) Gompertz, (vi) standard Cox proportional hazards model (CoxPH), and (vii) PTA model based on the above six models. For model estimation, the C-index and IBS of these seven AI models were displayed in the Table 2. The C-index of the PTA model was 0.854 and 0.801 in the train and validation cohorts, respectively, which were higher than other six AI models except for the RSF model in train cohort. Even though the RSF model achieved the highest C-index (0.926) in the train set, while in the validation cohort, the C-index was only 0.765, indicating the potential presence of over-fitting in the RSF model. Given the C-index of the train and validation cohorts, the PTA model derived from the above six algorithms outperformed other single-algorithm models. As expected, the IBS of the six single algorithms and PTA algorithm was far smaller than 0.25, demonstrating their capability for clinical application (Supplement 2-3).

Predictive performance of the PTA model

To further validate the PTA model, we drew the receiver operating characteristic curves (ROC) and calculated the AUC. The AUC values for 1 year, 3 years, and 5 years were 0.912 (95% confidence interval [CI], 0.887–0.938), 0.914 (95% CI, 0.891–0.937), and 0.928 (95% CI, 0.903–0.953), respectively (Supplement 4A-C and Supplement 5). In addition, the AUCs for TACE treatment were 0.893 (95% CI, 0.858–0.928), 0.857 (95% CI, 0.810–0.904), and 0.858 (95% CI, 0.787–0.929), whereas the AUCs for LR were 0.873 (95% CI, 0.805–0.941), 0.850 (95% CI, 0.797–0.903), and 0.839 (95% CI, 0.779–0.899) at 1, 3, and 5 years, respectively (Supplement 5). The full summary of all indicators (accuracy, sensitivity, specificity, positive predictive value [PPV], negative predictive value [NPV], positive likelihood ratio [PLR], and negative likelihood ratio [NLR]) were compiled in Supplement 5. These results suggested that the PTA model could accurately predict HCC survival at the observed follow-up time.

Additionally, the performance and discriminative ability of clinical guidelines (BCLC, BCLC B sub-classification, HKLC, and ITA.LI.CA stage), tumor-burden-based models (up-to-seven model, four-and-seven model, and six-and-twelve model), and models adopting other parameters (HAP score, mHAP II score, mHAP III score, ALBI score, and MESIAH score) were compared with the PTA model (Table 2). As expected, the 1-, 3- and 5-year auROC and C-index of the PTA model were higher than those of the above mentioned models and prognostic scores. Moreover, three calibration curves were plotted to show the predicted probabilities of death caused by HCC in 1, 3, and 5 years (Supplement 4D-F). The observed survival was within a negligible margin of error of the predicted survival, showing that the performance of the PTA model was overwhelmingly good.

Comparison with clinical guidelines

Next, we compared the discriminative performance of the PTA model in selecting potential candidates with that of the BCLC and HKLC guidelines. As stated above,

the LR and TACE candidates were determined following the BCLC and HKCL guidelines. Among the patients who underwent LR therapy (Supplement 6A-C), the PTA model identified 1386 potential LR candidates, BCLC guidelines selected 1196 cases, and HKCL chose 1765 candidate patients. K-M cures clearly showed that the survival difference between recommended and non-recommended populations was the largest in the PTA model compared with other guidelines. Meanwhile, the hazard ratio (HR) calculated by Cox regression analysis was 10.6, 2.02, and 1.93 respectively in the PTA model, BCLC, and HKCL guidelines (non-recommended as reference). Likewise, among the patients who accepted TACE, the PTA model, BCLC, and HKCL guidelines discriminated 323, 964, and 521 cases, respectively. The HR for the PTA model, BCLC, and HKCL guidelines was 25.4, 0.901, and 0.503, respectively (Supplement 6D-F).

Moreover, the LR candidates recommended by the PTA model had a prolonged OS compared to those suggested by BCLC and HKLC (Figure 2A); a similar conclusion was reached for the TACE group (Figure 2B). Intriguingly, the PTA model also found potential allocation “error” populations in the TACE and LR groups, depicted as hypothetical K-M curves (Figure 3A-B). The MST predicted by the PTA model was significantly higher compared with that of the original therapy allocation, suggesting that alternative therapies can enable patients to achieve a better prognosis and that mistaken allocation either to LR or TACE is still abundant. The patients with actual treatment and LR or TACE candidates are clearly shown in Figure 3C. Regarding the original LR allocation, 1458 cases had the right allocation, while 458 “model-found” cases were misled and should have been given TACE therapy. Similarly, there were abundant erroneous allocations among the original TACE allocations (2752, 89.5%).

Given that BCLC, the HKLC staging system, and PS could affect the prognosis of the potential benefit-gained population, we stratified patients into different BCLC subgroups (BCLC 0-A, BCLC B, and BCLC C stages; Supplement 7), HKLC subgroups (HKLC I-II and HKLC III; Supplement 8), and different PS (PS0 and PS1; Supplement 9). The PTA model could accurately select benefit-gained patients for LR

and TACE across different BCLC and HKLC stages and PS. Collectively, the K-M curves and HR consistently showed that the PTA algorithm could more effectively select TACE and LR candidates than the two authoritative therapeutic guidelines.

Web development and clinical application

To make an easy-to-apply tool and visualize the individual predictive results, we implemented the PTA models as a web interface, which could be freely accessed from www.pta4hcc.com. Users may input four groups of parameters: (a) demographic information, such as age and gender; (b) liver function; (c) tumor burden files; and (d) routine laboratory results like kidney function. The PTA model calculates the survival rate for each month when adopting different treatments (now including LR and TACE) and generates MST, all of which can be displayed on the user-friendly interface. For example, a 65-year-old man with hepatitis B virus infection and no prior treatment would possess a better prognosis if LR therapy was adopted instead of TACE after the diagnosis of HCC. His tumor burden characteristics are as follows: the number of tumors is four, the maximum tumor size is 8 cm, the AFP is 300 µg/L, and the ECOG or PS is 0. In addition, the information on the other two groups is also input into the website in the complete version. The output is his predicted survival curves derived from the PTA model, showing that LR's MST is 78 months, while TACE's MST is only 23 months (Supplement 10).

In parallel with the complete PTA algorithm, a concise version including the nine most important features was also developed on this website. This simple AI version could also calculate the integrated survival model immediately upon the input of these important features, especially for cases where some above-stated module features were unavailable. For example, a patient with two tumor lesions, a tumor size of 12 cm, 100 µg/L AFP, good PS, 120 g/L HGB, 35 U/L AST, 40 g/L ALB, and normal INR would benefit from TACE therapy rather than LR. The simulative survival curve indicates that the MST was 15 and 10 months for TACE and LR allocation, respectively (Supplement 11).

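### The under-30-days follow-up exclusion makes no exception for deaths, so as written no death can occur on days 0–29 although OS starts at the procedure

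*Combined protocol and SAP*

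**What the plan says.** All references are to the combined protocol and SAP.

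- **Section 1, Study population.** Exclusion (d) is a "duration of follow-up of fewer than 30 days". The term is not defined further, and nothing is said about patients whose follow-up was short because they died. The split comes after eligibility: "Eligible patients were randomly stratified into train and validation cohorts".
- **Section 6, Statistical analyses.** "Overall survival (OS) was defined as the time interval between initial TACE or LR and all-cause death". On censoring: "Patients who survived up to the last follow-up date (October 15th, 2021) or were lost to follow-up were censored". No day-30 landmark, delayed entry or sensitivity analysis is described.
- **Section 4, Model estimation.** Candidates are classed by a ratio of predicted median survival times (MST). For example, "ideal TACE candidates are those with an additional survival benefit of more than 50% compared to LR allocation".
- **Web development and clinical application.** "The PTA model calculates the survival rate for each month when adopting different treatments". In the concise-version example, "the MST was 15 and 10 months for TACE and LR allocation, respectively".

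**The concern.** A patient who dies on day 12 has 12 days of follow-up and meets criterion (d). Entry to the cohort then depends on the outcome: only people alive at day 30 are analysed, yet their time is counted from day 0. Days 0–29 contribute person-time and cannot contain an event.

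The rule is not needed for its likely purpose. Patients lost early or treated shortly before the cutoff are already censored under section 6. What (d) adds on the literal reading is the removal of early deaths. Deaths from day 30 onward, including treatment-related ones, stay in.

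The product is a tool for choosing between two procedures before either is done. If the earliest deaths are missing, its first-month survival and every later point are conditional on something unknown when the choice is made. If early mortality is similar in the two arms, the LR–TACE contrast barely moves. If it differs, the contrast shifts, and patients near the 50% MST threshold can change class.

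**Working it through.** **Inputs from the documents**
- Screened 5816 (section 1); included 4991, made up of LR 1916 and TACE 3075 (Basic clinical characteristics). 1916 + 3075 = 4991. Not included for any reason: 5816 − 4991 = 825.
- Survival at 1, 3 and 5 years (same heading): LR 91.7%, 79.6%, 70.8%; TACE 74.8%, 41.5%, 26.4%.

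**Assumed input**
- 30-day mortality m is not given; I take 1–3% per arm. For scale, a constant hazard through the reported 1-year survival gives a 30-day risk of 1 − 0.917^(30/365.25) = 0.7% for LR and 1 − 0.748^(30/365.25) = 2.4% for TACE.

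The plan has no figure of its own to reproduce here.

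**Step 1: survival from the procedure.** If early deaths were dropped, the reported figure is survival given alive at day 30, so S(t) from the procedure = (1 − m) × reported S(t).
- LR, 1 year: 0.917 × 0.99 = 0.908; 0.917 × 0.97 = 0.889.
- TACE, 1 year: 0.748 × 0.99 = 0.741; 0.748 × 0.97 = 0.726.
- LR minus TACE at 1 year: 16.9 points as reported; 88.9 − 74.1 = 14.9 (from unrounded values) at LR 3%/TACE 1%; 90.8 − 72.6 = 18.2 at LR 1%/TACE 3%.

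**Step 2: deaths removed.** The number is n × m/(1 − m), and the share of all 1-year deaths is m/(1 − S × (1 − m)).
- LR: about 19 (1%) to 59 (3%), or 11–27% of 1-year deaths.
- TACE: about 31 to 95, or 4–11% of 1-year deaths.

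**Step 3: ratio of group medians.** Log-linear interpolation between the reported time points after multiplying by (1 − m). LR is extrapolated beyond 60 months at its 36–60 month hazard, ln(0.796/0.708)/24 = 0.00488 per month. The TACE hazard between 12 and 36 months is ln(0.748/0.415)/24 = 0.02455.
- LR median = 60 + ln(0.708 × (1 − m)/0.5)/0.00488
- TACE median = 12 + ln(0.748 × (1 − m)/0.5)/0.02455

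| m, LR / TACE | LR median (months) | TACE median (months) | Ratio | Change |
|---|---|---|---|---|
| 0 / 0 | 131.3 | 28.4 | 4.62 | – |
| 3% / 3% | 125.0 | 27.2 | 4.60 | −0.4% |
| 3% / 1% | 125.0 | 28.0 | 4.46 | −3.4% |
| 1% / 3% | 129.2 | 27.2 | 4.76 | +2.9% |

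Ratios are from unrounded medians.

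**Step 4: one patient near the threshold.** With exponential survival, the MST from the procedure = conditional MST × (1 + log2(1 − m)), a factor of 0.9855 at 1% and 0.9561 at 3%. The web example has TACE 15 and LR 10 months, ratio 1.50.
- Equal early mortality: 1.50.
- LR 3%/TACE 1%: 14.78/9.56 = 1.55.
- LR 1%/TACE 3%: 14.34/9.86 = 1.46.

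**The case against.** **The term is undefined.** Follow-up could mean potential follow-up to the cutoff, or the rule may have been applied only to patients lost early. On either reading no death is removed. The text states neither, and observed time to death or last contact is the ordinary meaning. It does stand that the data may be unaffected: the wording is certain, a bias in the data is not.

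**Figure 1 and Supplement 1 were not available.** The flow chart may break down exclusions by criterion, and the supplement holds the preprocessing details. This also stands. The statements about missing counts and missing landmark or sensitivity analyses apply only to the text available.

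**The effect is small.** The group median ratio moves by a few percent from 4.62, far from 1.5, and the LR median is extrapolated to more than twice the last reported time point. I agree that the group-level effect is modest.

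**The single-patient example is weak.** If the months are rounded to whole numbers, the ratio could lie anywhere from 14.5/10.5 = 1.38 to 15.5/9.5 = 1.63, which covers the whole computed shift. The documents do not apply the 50% rule to this patient, and TACE keeps the longer MST in every scenario. The example shows only how sensitive a case near the threshold can be.

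None of this removes the conflict between an entry rule that conditions on 30-day survival and a clock that starts at day 0.

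**Conclusion.** The concern holds as worded. Followed literally, criterion (d) selects on the outcome in both the training and validation data, and the internal validation cannot reveal it. If deaths were removed, each affected arm's survival is overstated: at an assumed 1–3% 30-day mortality, by 0.9–2.8 points for LR and 0.7–2.2 points for TACE at 1 year. The LR–TACE contrast changes little with equal early mortality and by about 3% in the median ratio with 3% against 1%. Its direction cannot be told from the documents. The number of deaths removed may be zero. This should be fixed because the output is meant for patients before treatment, and a reader cannot now tell which population the curves describe.

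**What to change.** 1. Define duration of follow-up, and report the patients excluded under (d) by arm and vital status.
2. Reword (d): keep patients from the day of the procedure, count deaths before day 30 as events, and censor those alive with short follow-up. If an administrative limit is wanted, set it by treatment date relative to 15 October 2021, not by observed follow-up.
3. If none of the excluded patients had died, correct the wording and stop there.
4. If some had died, restore those who meet the other criteria, including complete clinical information, then refit the PTA model and update the survival figures, performance measures and web tool.
5. If they cannot be recovered, start the clock at day 30 and label every survival figure and web prediction as conditional on surviving 30 days.

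The first step is a count from records already screened. A refit is needed only if deaths were excluded. The downside is some re-analysis and slightly lower stated survival in any arm where deaths are restored.

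### The random patient-level split almost certainly puts the same hospitals in both sets, and none is described as held out, so the reported performance does not show how the public web tool works at a new hospital

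*Combined protocol and SAP*

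**What the plan says.** Section 1 (Study population) gives the source: "a total of 5816 consecutive HCC patients receiving LR or TACE from 15 Chinese tertiary hospitals were retrospectively screened". It then describes the split: "Eligible patients were randomly stratified into train and validation cohorts (ratio=0.85: 0.15". No stratification factor is named.

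The results text (Basic clinical characteristics) reports that "4991 patients met the selection criteria and were included" and that "4192 (84%) and 799 (16%) patients were divided into train and validation sets, respectively". By treatment, the training set holds 1622 LR and 2570 TACE patients, and the validation set 294 and 505.

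Section 3 (Model development) guards against overfitting by K-fold cross-validation inside the training cohort. It states neither K nor any grouping by hospital. The results give the ensemble (PTA) model a C-index of 0.854 in training and 0.801 in validation, with no confidence interval.

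Section 5 (Web implementation) puts the model online once training and validation are done and names no further check. The results (Web development and clinical application) describe the interface as one "which could be freely accessed from www.pta4hcc.com".

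**The concern.** A random draw of patients from a pooled multicentre cohort gives a validation set with the same hospitals, calendar period and local habits of choosing between resection (LR) and TACE as the training set. Agreement between the two sets shows that the model reproduces itself in those hospitals. It does not show that predictions hold where none of the patients contributed to training.

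That second question matters because of how the model is used. Any visitor to the website receives predicted LR and TACE median survival for an individual patient. The results also go beyond internal performance: they present the model as fit for clinical use, as better than two guidelines at selecting candidates, and as showing that many past allocations were wrong. Those allocation counts cover the whole cohort (1458 + 458 = 1916 LR; 323 + 2752 = 3075 TACE), so they include training patients.

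Treatment type is a model input. If case mix, treatment selection or technique differs between hospitals, calibration and the comparison between the two predicted curves could shift at a new site. The present design cannot detect this.

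**Working it through.** **1. The plan's own figure: the size of the split.**
- Planned: 0.15 × 4991 = 748.65, or 749 patients. Reported: 799, and 799/4991 = 16.01%. The 0.85:0.15 ratio is not reproduced.
- A fixed 16% split reproduces it: 0.16 × 4991 = 798.56, rounded up to 799.
- The counts add up: 1622 + 2570 = 4192; 294 + 505 = 799; 4192 + 799 = 4991.
- Validation share by treatment: LR 294/1916 = 15.3%; TACE 505/3075 = 16.4% (Fisher P = 0.32). This is compatible with a random draw of patients. An exact split stratified on treatment would give 0.1601 × 1916 ≈ 307 LR patients, not 294.

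The mismatch of 749 against 799 should be reconciled, but it does not affect this point.

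**2. Do the same hospitals appear in both sets?** No counts by hospital are given. The equal-size average is 4991/15 ≈ 333 patients, of whom 799/15 ≈ 53 would be in validation. With p = 799/4991 = 0.160 and independent assignment, P(no validation patient) = (1 − p)^n for a hospital with n included patients:
- n = 10: 17%
- n = 20: 3.1%
- n = 30: 0.5%
- n = 50: 0.02%
- n = 100: 3 × 10⁻⁸

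The chance that all 15 hospitals are in both sets is the product over hospitals of 1 − (1 − p)^n − p^n. In each assumed case the other hospitals share the remaining patients equally:
- equal sizes: about 1.00
- five hospitals of 30 patients: 0.97
- five of 20: 0.86
- three of 10: 0.56

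Overlap is thus near certain for any hospital with about 50 or more included patients, but not guaranteed for very small ones. Stratifying by hospital would make the overlap deliberate. Only drawing whole hospitals would remove it, and the text describes no such draw.

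**3. What uncertainty do the reported intervals carry?** The 1-year AUC is 0.912 (0.887–0.938), so SE = (0.938 − 0.887)/3.92 = 0.013. The data set is not stated. A Hanley–McNeil approximation, with 1-year deaths taken from the overall survival rates (294 × 0.083 + 505 × 0.252 ≈ 152 in validation), gives an SE of 0.016 for n = 799 and 0.007 for n = 4192. The AUCs therefore most likely come from the validation set. As far as the text shows, the interval reflects sampling of patients and not variation between hospitals.

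**4. Illustration of what is left out.** The documents give no between-hospital SD (τ) and no SE for the C-index. Assume SE = 0.012 (close to the 0.013 above) and τ = 0.02 to 0.04. The 95% half-width for a new hospital is 1.96 × √(SE² + τ²):
- τ = 0: 1.96 × 0.012 = 0.024
- τ = 0.02: 1.96 × √(0.000144 + 0.0004) = 0.046, or 0.755 to 0.847 around 0.801
- τ = 0.04: 1.96 × √(0.000144 + 0.0016) = 0.082, or 0.719 to 0.883

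**The case against.** A random split is a legitimate form of internal validation, and the visible text never calls it external. That stands: the fault lies in the distance between the design and the public use of the tool, not in the split itself.

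The evidence that hospitals differ is thin. The wide TACE drug ranges in Section 2 are pooled over patients and could reflect tailoring within one hospital. This also stands; variation between hospitals is plausible but not shown.

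The illustrative interval rests on assumed inputs, and even its lowest value, 0.801 − 0.082 = 0.719, exceeds the C-index threshold of 0.7 in Section 3. That is correct, but the threshold is a rule for retaining algorithms. It says nothing about calibration or about the LR and TACE median survival shown to users.

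Supplement 1 and Figure 1 were not available for this review and may give hospital counts or further detail on the split.

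Two stronger readings are tempting. A reader might infer that every one of the 15 hospitals is in both sets. The documents do not establish this: 15 is the number of hospitals where patients were screened, and counts of included patients by hospital are missing. A reader might also infer that the model performs worse elsewhere. Nothing reported shows that either; the question is untested.

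**Conclusion.** The point holds as a limit on what the reported performance can support, together with a cheap improvement. It is not a demonstrated error in the model. It needs only that patients were split at random and that no hospital is described as held out or reported separately; it does not need overlap at all 15 sites. The C-index of 0.801, the AUCs and the calibration curves should be read as performance within the contributing hospitals.

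The size of any shortfall at a new hospital is unknown. The half-widths above show only how much wider an honest interval could be under the assumed inputs, compared with 0.024 from patient sampling alone. The conclusion does not depend on them. It would change if the unseen supplements described a hospital-level hold-out or a separate cohort.

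**What to change.** Keep the random split and add internal–external validation on the existing data:

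- Repeat the full PTA development procedure, including tuning and the ensemble step, leaving out one hospital at a time and pooling hospitals with few events. Write down K and the tuning rules first, so that each repeat follows the same procedure.
- Report the number of patients and deaths by hospital, the per-hospital and pooled C-index, the calibration slope and intercept at 1, 3 and 5 years, and a prediction interval for a new hospital.
- Show these beside the random-split result in the report and on the website.
- State in both places that no fully external validation has been done, and that this check covers neither a later period nor settings other than these tertiary hospitals. The website statement can be made at once.

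The cost is up to 15 repeats of tuning and refitting a six-model ensemble, which is more than 15 simple refits, and it requires a hospital identifier in the data set. No new patients are needed. The C-index will probably be lower and more variable than 0.801.
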